5.3.1.4. Other efficacy variables

5.3.1.4.1. NEDA-3 status up to extension EOS

No evidence of disease activity (NEDA)-3 up to extension EOS is defined by the absence of confirmed relapse, Gd+ T1 lesions, new or enlarging T2 lesions, and 12-week CDA. If at least one of the criteria is not fulfilled or the subject discontinues treatment prematurely, the subject is not considered to have achieved NEDA-3.

Derivation details

A subject is considered as having evidence of disease activity if at least one of the following applies:

- Any confirmed relapse up to extension EOS.
- Presence of Gd+ T1 lesions during the course of study until extension EOS.
- Presence of new or enlarging T2 lesions during the course of study until extension EOS.
- Any 12-week CDA up to extension EOS.

Subjects that discontinue treatment prematurely are considered as showing evidence of disease activity, irrespective of what the reason for treatment discontinuation is.

Subjects without evidence of disease activity as defined above, who have missing outcome for any component (absence of confirmed relapse up to extension EOS, absence of new Gd+ T1 lesions from Core baseline to Extension EOS, absence of new or enlarging T2 lesions from Core baseline to Extension EOS) are considered to have missing outcome for NEDA-3.

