1.2.3.1. End-of-treatment visit

The EOT visit will take place at Week 240 or at the time ponesimod is commercially available for treatment of MS in the subject's country (whichever occurs first). The EOT visit should preferably take place 1 day after the last dose of study treatment but no later than 14 days after the last dose of study treatment. The EOT visit may take place in case:

- of premature discontinuation of study treatment for subjects meeting the study specific criteria for permanent discontinuation of study treatment;
- the sponsor decides to stop the extension study;
- the subject or the investigator decides to discontinue the study treatment;
- ponesimod is commercially available for the treatment of MS in the subject's country.

In some countries, additional reimbursement negotiations and central formulary approvals will be needed before ponesimod becomes available. In this case, subjects participating in the AC-058B303 study can continue to receive ponesimod until ponesimod is available in their respective country, or for a maximum of 240 weeks. Subjects will get access to the study drug for a maximum of 240 weeks*. If ponesimod becomes available locally before the end of the 240 weeks in the AC-058B303 extension study, then subjects will be considered as having completed the extension study and will be switched to commercially available supply if they wish to continue ponesimod treatment. For these subjects, the switch to commercially available ponesimod should occur at the EOT visit, and commercially available ponesimod may be initiated on the day following last intake of study treatment.

[figure not shown]
*except for subjects in Ukraine where the maximum treatment duration will be 288 weeks (or not later than preplanned global Last Subject Last End of Treatment in Q4 2023)

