5.1.10. Re-assignment of EOT visits / visit windowing

For core study, analysis visits are used as derived in the core study and are not re-derived for the extension analysis.

Extension study

If a subject discontinued study drug prematurely, as defined in Section 5.4.1.1.5, the EOT visit will be considered as the premature EOT visit. This rule also applies to subjects who are treatment completers but switched to commercial ponesimod prior to Week 240.

For all parameters unless stated below: For subjects who discontinued study drug prematurely with available premature EOT visit and subjects who switched to commercial ponesimod, the visit may be re-assigned to a scheduled visit as follows:

• If a result is missing for a scheduled visit, it can be replaced with a result from a premature EOT visit available in the respective visit window [see Table 7].

Table 7: Premature End-of-Treatment remapping

Visit window	Nominal value Day	Lower limit for Day	Upper limit for Day
Week 2	15	2	22
Week 4 (Except LB)	29	23	70
Week 12 (Except LB)	85	71	126
Week 4* (For LB only)	29	23	42
Week 8* (For LB only)	57	43	70
Week 12* (For LB only)	85	71	98
Week 16* (For LB only)	113	99	126
Week 20* (For LB only)	141	127	154
Week 24* (For LB only)	169	155	210
Week 24 (Except LB)	169	127	210
Week 36	253	211	294
Week 48	337	295	378
Week 60	421	379	462
Week 72	505	463	546
Week 84	589	547	630
Week 96	673	631	714
Week 108	757	715	798
Week 120	841	799	882
Week 132	925	883	966
Week 144	1009	967	1050
Week 156	1093	1051	1134
Week 168	1177	1135	1218
Week 180	1261	1219	1302
Week 192	1345	1303	1386
Week 204	1429	1387	1470
Week 216	1513	1471	1554
Week 228	1597	1555	1638
Week 240	1681	1639	Open end** / 1722***
Week 252***	1765	1723	1806
Week 264***	1849	1807	1890
Week 276***	1933	1891	1974
Week 288***	2017	1975	Open end

Day refers to treatment day, i.e., days from extension study treatment start.

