5.2.2. Analysis of subject disposition

5.2.2.1. Subject disposition

Frequency counts and percentages for all the following variables will be presented in a summary table by core treatment group and overall based on the FAS:

Core study:

- Subjects randomized in the core study;
- Subjects treated in the core study;
- Subjects prematurely discontinued treatment in the core study;

- Subjects completed treatment in the core study;
- Subjects prematurely discontinued from the core study;
- Subjects completed the core study per protocol;
- Subjects completed the core treatment and study per protocol;
- Subjects completed the core treatment and study as protocol and did not enroll in the extension study.

Extension study:

- Subjects enrolled in the extension study;
- Subjects treated in the extension study;
- Subjects prematurely discontinued treatment in the extension study;
- Subjects interrupted treatment for planned pregnancy;
- Subjects completed treatment in extension study (further split into: "Completed as per protocol" or "Approved Drug Available For Indication");
- Subjects prematurely discontinued from the extension study;
- Subjects completed the extension study;
- Subjects completed the extension treatment and study per protocol;
- Subjects prematurely discontinued from treatment or study in the extension study.

The denominator for percentages for core study variables above will be based on the number of randomized subjects in the core study. The denominator for percentages for the extension study variables above will be based on the number of enrolled subjects in the extension study (except for the percentage of 'enrolled in the extension study', which will be based on the number of randomized subjects in the core study).

A subject disposition flow-chart will be produced including all the disposition information listed above.

The number and percent of subjects in the EXTS are summarized by country and site, by core study treatment group, and overall.

All subject disposition variables will be presented in a dedicated listing.

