5.3.2.5. Analysis of other efficacy variables

5.3.2.5.1. **NEDA-3** status up to **EOS**

Descriptive statistics of NEDA-3 status (Yes, No, Missing) up to Extension EOS including its components ([i] Presence of confirmed relapse, [ii] Presence of Gd+ T1 lesions, [iii] Presence of new or enlarging T2 lesions, [iv] 12-week CDA event, or [v] premature treatment discontinuation) will be presented using the EXTS. A listing will be prepared.

5.3.2.5.2. **NEDA-4** status up to EOS

NEDA-4 status up to Extension EOS will be analyzed in the same way as NEDA-3 status on the EXTS.

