5.4.1.1.5. Study treatment completion/discontinuation

Discontinuation from study treatment in the core study is used as derived in the core study. See the core study SAP for details.

Study treatment discontinuations in the extension study are collected on the extension eCRF page 'Premature Discontinuation of Study Treatment'.

A premature permanent treatment discontinuation in the extension study is defined as permanently stopping treatment prior to the extension EOT visit (Week 240/Week 288 for those Ukraine subjects, or at the time ponesimod is commercially available for treatment of MS in the subject's country, whichever occurs first).

Reasons for premature treatment discontinuation in the extension study are as follows:

- Death:
- Lost to follow-up;
- Pre-specified study treatment discontinuation criteria;
- Subject decision (further split into: Adverse event, Lack of efficacy, No reason provided, Other);
- Physician decision (further split into: Adverse event, Lack of efficacy, Other);
- Sponsor decision (further split into: Study termination, Other).

Study treatment completion records are collected on the extension eCRF page "Maintenance Ponesimod" where fields "Completed as per protocol" or "Approved Drug Available For Indication" are entered.

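### NEDA-3/4 up to extension EOS is one status over unequal follow-up: commercial switchers can score Yes at any duration while other early stoppers score No, so the proportion partly reflects local launch dates

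*SAP*

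**What the plan says.** Section 1.1.2.1 (Table 3) lists NEDA-3 and NEDA-4 among the main clinical endpoints. Sections 5.3.1.4.1 and 5.3.1.4.2 define each as one status per subject up to extension EOS. Any premature treatment stop is a failure: "Subjects that discontinue treatment prematurely are considered as showing evidence of disease activity, irrespective of what the reason for treatment discontinuation is". The planned analysis in section 5.3.2.5.1 is "Descriptive statistics of NEDA-3 status (Yes, No, Missing) up to Extension EOS including its components", on the EXTS; NEDA-4 is handled in the same way.

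Section 5.4.1.1.5 decides who is premature. It defines premature discontinuation as "permanently stopping treatment prior to the extension EOT visit (Week 240/Week 288 for those Ukraine subjects", with the alternative endpoint "or at the time ponesimod is commercially available for treatment of MS in the" subject's country, whichever is first. A stop at launch is therefore not premature. Three other places agree:

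- Section 1.2.3.1: if the drug becomes available locally before 240 weeks, "then subjects will be considered as having completed the extension study and will be switched to commercially available supply".
- Section 5.2.2.1: treatment completers are split to include "Approved Drug Available For Indication".
- Section 5.1.10: "This rule also applies to subjects who are treatment completers but switched to commercial ponesimod prior to Week 240". This borrows the premature-EOT rule for visit windowing and still calls these subjects completers.

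For Ukraine, the footnote in section 1.2.3.1 says the "maximum treatment duration will be 288 weeks (or not later than preplanned global Last Subject Last End of Treatment in Q4 2023". Section 5.4.1.1.5 gives only Week 288 for these subjects and does not mention the Q4 2023 limit.

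**The concern.** Two subjects with the same disease course and the same follow-up can receive opposite statuses, and two with very different follow-up can receive the same one. A binary status taken at each subject's own end of study has no common horizon. With disease control held fixed, its Yes proportion rises when ponesimod launches earlier in the participating countries.

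At stake is the absolute long-term NEDA proportion, which a reader of the study report would naturally take as a measure of disease control over the full extension. It could not safely be set beside a fixed-time NEDA figure, or compared between countries with different launch dates. The concern is not with counting discontinuation as failure in itself, which is a recognised conservative choice. It is that this rule is combined with a completion date set by an external event, and nothing in the analysis accounts for time.

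**Working it through.** **1. Trace the rule.** Take a subject free of activity at extension Week 96, with the MRI components available.

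| What happens next | Premature under 5.4.1.1.5? | NEDA-3 |
|---|---|---|
| Local launch, switches to commercial supply | No | Yes |
| Stops at Week 96 by sponsor decision or for a personal reason | Yes | No |
| Continues to Week 240 | No | Yes only if still activity-free at the end |

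**2. Compare with the related outcomes.** ARR uses log time in study as an offset (5.3.2.2.1). Time to first relapse and to CDA use Kaplan-Meier with censoring (5.3.1.1.2, 5.3.1.3.2, 5.3.2.4.1). Cumulative T2 lesions and cumulative CUAL use log time to last MRI (5.3.2.3.2, 5.3.2.3.3). NEDA is built from relapse, lesion and CDA outcomes but has no adjustment for time, no fixed-time version and no split by completion type.

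**3. Illustrate the size.** The SAP states no NEDA proportion, so there is no figure to reproduce.

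*From the SAP:* 108 core weeks (1.2) and up to 240 extension weeks (1.2.3).

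*Assumed, not in the SAP:* a constant hazard h of first activity of 0.1, 0.2 or 0.3 per year; 50% of subjects switching, all at extension Week 96 or all at Week 192; no premature stops; no missing components. The gap between the studies and the safety follow-up are ignored.

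Follow-up in years = (108 + extension weeks) × 7 / 365.25:

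- Week 96: 204 × 7 / 365.25 = 3.91
- Week 192: 300 × 7 / 365.25 = 5.75
- Week 240: 348 × 7 / 365.25 = 6.67

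P(NEDA) = exp(−h × years). Pooled Yes = 0.5 × P(Week 240) + 0.5 × P(switch week).

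| h per year | P at Week 96 | P at Week 192 | P at Week 240 (no switching) | Pooled, 50% at Week 96 | Pooled, 50% at Week 192 |
|---|---|---|---|---|---|
| 0.1 | 67.6% | 56.3% | 51.3% | 59.5% (+8.2) | 53.8% (+2.5) |
| 0.2 | 45.8% | 31.7% | 26.3% | 36.0% (+9.7) | 29.0% (+2.7) |
| 0.3 | 30.9% | 17.8% | 13.5% | 22.2% (+8.7) | 15.7% (+2.2) |

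Disease control is identical along each row; only the switching pattern differs. With 25% switching the shifts at h = 0.2 are 4.9 points (Week 96) and 1.4 points (Week 192). Adding an assumed premature-stop hazard of 0.10 per year in the extension, counted as failure, the h = 0.2 figure goes from 16.6% with no switching to 27.3% (50% at Week 96) or 19.3% (50% at Week 192).

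**4. Ukraine cap.** 288 weeks × 7 = 2016 days. Counting back from 31 December 2023, the latest date in Q4 2023, gives 24 June 2018. A subject starting the extension after that date cannot complete 288 weeks under the cap. Read literally, section 5.4.1.1.5 would class such a subject as premature and hence a NEDA failure. The SAP gives no Ukraine start dates, so the number affected is unknown.

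**The case against.** The strongest reply is that the endpoint is labelled as status up to extension EOS and is never presented as a Week-240 probability. All analyses are exploratory (section 2), and no regional NEDA comparison is planned. Much of the context is reported elsewhere: time in study by category (5.2.4), completers split by reason (5.2.2.1), premature discontinuation shown as a NEDA component (5.3.2.5.1), Kaplan-Meier for relapse and CDA, and lesion absence by visit. That stands and limits the harm. But the component display shows the discontinuation failures and not the shorter follow-up of switchers, and marginal results for the components cannot be recombined into the composite.

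Three stronger readings are tempting and not supported.

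- *Every activity-free switcher scores Yes.* Sections 5.3.1.2.1 and 5.3.1.2.2 set lesion absence to missing for a lesion-free subject with no MRI result at a visit that is not named. If Week 240 is meant, early switchers become Missing. The subject's own final scan is the more natural reading, because the endpoint runs to own EOS and switchers' EOT scans are remapped to earlier visits. The text does not settle it, and the result depends on launch dates under either reading.
- *The comparison of core arms is biased.* Launch is a country-level event, and nothing in the SAP shows that it falls unequally on the arms.
- *Ukraine subjects will be scored as failures.* Section 5.4.1.1.5 also says that completion is collected on the eCRF as an explicit record, so a subject stopped by the cap may well be entered as completed per protocol. What is shown is two sections that do not agree, not a demonstrated misclassification.

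A Week-96 switch is also the less favourable illustration. The SAP supports it no more than Week 192, where the shift is only 2 to 3 points.

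**Conclusion.** The point holds for the absolute NEDA-3/4 proportions. They mix horizons set partly by local launch dates and do not estimate the probability of being activity-free at any stated time. The direction follows from the definitions: if switchers' components are not missing, earlier or more frequent switching raises the Yes proportion at unchanged disease control.

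The size is unknown. The illustrated range of about 2 to 10 points rests on constant hazards of 0.1 to 0.3 per year, 50% switching between Week 192 and Week 96, no premature stops and switching unrelated to prognosis. None of these comes from the SAP. As the endpoint is descriptive, this is an interpretability problem in a main clinical endpoint and does not invalidate an inference. The Ukraine wording is a secondary inconsistency that needs reconciling.

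**What to change.** 1. Add NEDA-3 and NEDA-4 as time from core randomization to first evidence of activity or premature discontinuation. Censor commercial switchers at their last adequate MRI/EDSS assessment; censoring at EOS would credit time without a scan. Report estimates at core Week 108 and extension Weeks 48, 96, 144, 192 and 240.
2. State two limits beside the results. Lesion event times are known only to the interval between scans, about 48 weeks in the extension. Censoring assumes that launch date is independent of prognosis.
3. Keep the EOS status table as supportive, split by completion type and with follow-up time shown.
4. In sections 5.3.1.2.1 and 5.3.1.2.2, name the visit at which a missing MRI makes the lesion component missing.
5. Reconcile the completion definition in section 5.4.1.1.5 with the Ukraine limit in section 1.2.3.1, so that the derivation does not turn a stop imposed by that limit into a premature discontinuation and hence a NEDA failure.

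The cost is SAP wording, one derivation from dates already collected, and one added table. Estimates at late visits will probably be lower than the EOS proportion and have wider intervals.

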5.3.1.4.2. NEDA-4 status up to extension EOS

No evidence of disease activity (NEDA)-4 up to EOS is defined by the absence of confirmed relapse, Gd+ T1 lesions, new or enlarging T2 lesions, 12-week CDA until EOS, and absence of

annual brain volume decrease $\geq 0.4\%$ at all assessments from Core Baseline up to Extension EOS. If at least one of the criteria is not fulfilled or the subject discontinues treatment prematurely, the subject is not considered to have achieved NEDA-4.

Derivation is as for NEDA-3, but in addition a subject is considered as having evidence of disease activity if the following applies:

• Annual brain volume at any assessment from core baseline to extension EOS decrease ≥ 0.4%. The annual brain volume change is defined in Section 5.3.1.2.4. If at any visit the percentage change is <= -0.4% then the criteria "Annual brain volume decrease ≥ 0.4%" is met

5.3.1.4.3. Change in Multiple Sclerosis Functional Composite (MSFC) Z-score from baseline by visit up to Extension EOS

The Multiple Sclerosis Functional Composite (MSFC) score consists of 3 clinical examinations: Timed 25-Foot Walk, 9-Hole Peg Test (9-HPT), and Paced Auditory Serial Addition Test (PASAT-3" version). The timed 25-foot (7.62 meters) walk is a quantitative measure of lower extremity function. The 9-HPT is a quantitative measure of upper extremity (arm and hand) function. The PASAT is a measure of cognitive function that specifically assesses auditory information processing speed and flexibility, as well as calculation ability.

MSFC will be assessed at pre-randomization (3 tests conducted on 3 days apart, where the first 2 are considered practice tests) and at post-baseline Visits as scheduled in the protocol.

For each assessment, the MSFC score will be calculated as the mean of the Z-scores of the 3 components:

- (1) Timed 25-Foot Walk (T25FW) score (s)
- (2) 9-Hole Peg Test (9-HPT) score (s)
- (3) Paced Auditory Serial Addition Test (PASAT-3) score (Number correct).

Details for generating the MSFC Z-score and how to handle missing data are given in Section 6.14.1.

For analysis, baseline and nominal post-baseline visits are considered. See Section 5.1.10 for remapping of premature end of treatment or unscheduled visits (includes unscheduled visits due to relapse).

Baseline is defined as the last available MSFC score prior to or on randomization date. While this should usually present the subject's 3rd test, if that is missing, results from the practice test may be used. A flag is added indicating the number of tests conducted up to the baseline test inclusive.

5.3.1.4.4. Change in the symbol digit modalities test (SDMT) score from baseline by visit up to Extension EOS

The symbol digit modalities test (SDMT) measures attention and processing speed much like the PASAT. It is administered along with the MSFC at pre-randomization (3 tests, where the first 2 are considered practice tests) and at post-baseline visits as scheduled.

For analysis, baseline and nominal post-baseline visits are considered. See Section 5.1.9 for remapping of premature end of treatment or unscheduled visits.

Baseline is defined as the last available SDMT score prior to or on randomization date. While this should usually present the subject's 3rd test, if that is missing results from the practice test may be used. A flag is added indicating the number of tests conducted up to the baseline test inclusive.

5.3.2. Analysis Methods

5.3.2.1. Statistical methodology

5.3.2.1.1. Statistical methodology for count data

Count data will be analyzed assuming data is negative binomially (NB) distributed.

A generalized linear model with NB distribution will be assumed.

t_j denotes the length of observation (time in study) for subject j.

Y_j denotes the number of relapses for subject j during t_j.

 μ_i denotes the mean of the NB distribution of Y_i .

The mean for the distribution of the ARR for subject j, denoted by μ_j/t_j , will be modeled by the following equation:

$$\log (\mu_j / t_j) = \mathbf{x}_j' \mathbf{\theta}$$
, i.e., $\log (\mu_j) = \mathbf{x}_j' \mathbf{\theta} + \log (t_j)$, where

 \mathbf{x}_i is the vector denoting study treatments and covariates for subject j

 θ is the vector of unknown fixed-model parameters.

The SAS code for the NB model is as follows:

```
proc genmod data=ADREL;
  model relnum_r = / dist=negbin link=log offset = log(Time);
run;
```

If the model does not converge the Poisson distribution will be used instead of the negative binomial distribution.

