5.3.2.2. Analysis of relapse-related variables

5.3.2.2.1. Main analysis of ARR

The main statistical analysis will be performed on the FAS and EXTS using all data in the Combined Analysis Period. The model described in Section 5.3.2.1 for confirmed relapses will be used, with core study treatment as a factor and the logarithm of time in study (in years) from randomization up to the end of the Combined Analysis Period as an offset variable. ARR will be summarized descriptively by core treatment group in a table for confirmed relapses as follows:

- Number of confirmed relapses per subject: descriptive statistics;
- Number of confirmed relapses per subject: frequency counts and percentages for categories 0, 1, 2, 3, 4, 5-10 and 11+;
- Total number of confirmed relapses: frequency count:
- Total time in study (subject years): sum;
- Raw ARR: total number of confirmed relapses / total time in study.

Mean model-based estimates of the ARR (for confirmed relapses), by core study treatment group, as well as 95% CIs will be presented. A rate ratio comparing ponesimod with teriflunomide 14 mg will be derived from the model including 95% CIs.

The fit of the model will be assessed and other distributions such as the Poisson distribution will be considered in case of a lack of fit.

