5.3.2.2.2. Additional analyses of ARR

All relapses will be analyzed for the Combined Analysis Period on the FAS and EXTS as described in Section 5.3.2.1.1, i.e., including the first summary table described (and adding the ARR estimate and 95% CI from a NB model).

This approach will also be used to analyze confirmed relapses on:the Extension Analysis Period using the EXTS and the EXTS and for all relapses on:

• the Extension Analysis Period using the EXTS;

with the logarithm of the appropriate observation time during the related period as an offset variable.

Additionally, for confirmed relapses, the ARR estimate and 95% CI from a Poisson model (as the NB model is not expected to converge for all time periods) will be determined by 24-week period (as defined in Section 5.3.1) using FAS and EXTS as follows. The log of observational time during each interval will be used as offset.

- Core Analysis Period (core weeks 0-24, 24-48, 48-72, 72-96, 96-core EOS);
- Extension Analysis Period (extension weeks 0-24, 24-48, 48-72, 72-96, 96-120, 120-144, 144-168, 168-192, 192-216, 216-Extension EOS).

A line plot will be created to present the ARR estimate and the corresponding 95% CI by 24 weeks period.

Relapse characteristics will be summarized using descriptive statistics for the Combined Analysis Period on the FAS and for the Extension Analysis Period on the EXTS. This includes the following:

- Number (%) of subjects with at least one: relapse, relapse requiring hospitalization, relapse treated with corticosteroids; for all relapses up to EOS/cut-off and for confirmed relapses up to EOS/cut-off.
- Number (%) of relapses (out of total number of relapses) requiring hospitalization, treated with corticosteroids and descriptive statistics for continuous data for relapse duration (days); for all relapses up to EOS as well as for confirmed relapses up to EOS.

Full details of all relapses will be presented in a listing.

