5.3.2.3. Analysis of MRI-related variables

5.3.2.3.1. T1 Gd+ lesions

The total number of Gd+ T1 lesions per visit will be summarized descriptively as continuous data and in categories (anticipated categories: 0, 1, 2, 3, 4, 5, 6-10, 10+), for the Combined Analysis Period on the EXTS.

Descriptive statistics on absence of Gd+ T1 lesions (frequency and percentages of subjects with lesions absent, present) will be presented by visit, and cumulative for absence of Gd+ T1 lesions from Core baseline up to extension EOT will be tabulated. This analysis will be done for combined period using EXTS.

The total number of Gd+ T1 lesions will be analyzed by visit for the Combined Analysis Period on the EXTS using a negative binomial regression model: the response variable is the number of lesions at the respective visit, with core study treatment as a factor and no offset. Mean model-based estimates and corresponding 95% CIs will be presented. The corresponding plots will also be presented.

Total volume of T1 hypointense lesions and the change from core baseline per visit is summarized descriptively based on observed data, for combine analysis period using the EXTS. In addition, total volume of T1 hypointense lesions and the change from extension baseline per visit is summarized descriptively for extension period using EXTS. The total volume of T1 hypointense lesion data will be listed using FAS.

Descriptive statistics of the proportions of Gd+ T1 lesions at core baseline evolving to persistent black holes will be presented by visit in the subset of subjects with Gd+ T1 lesions present at baseline using the EXTS for combined period. Same analysis in relative to extension baseline (i.e. Core study EOT) will be repeated using EXTS during extension period. A listing will be prepared using the FAS.

Gd+ T1 lesions data will be listed on the FAS.

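### The three Poisson rules for the count models carry no overdispersion correction, and Poisson is wrongly named as a remedy for poor negative binomial fit

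*SAP*

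**What the plan says.** Section 5.3.2.1.1 sets the general rule: "Count data will be analyzed assuming data is negative binomially (NB) distributed". Plain Poisson then enters in three places.

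- **Non-convergence, section 5.3.2.1.1:** "If the model does not converge the Poisson distribution will be used instead of the negative binomial distribution". The notation there is written for relapses, but the section covers count data in general, and the MRI sections (5.3.2.3.1 to 5.3.2.3.3) use NB models without a fallback of their own.
- **By design, section 5.3.2.2.2:** confirmed relapses by 24-week period are to be reported as "the ARR estimate and 95% CI from a Poisson model (as the NB model is not expected to converge for all time periods").
- **Lack of fit, section 5.3.2.2.1:** for the main relapse-rate model, "other distributions such as the Poisson distribution will be considered in case of a lack of fit". No criterion for lack of fit is given.

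No scale parameter or robust variance is mentioned in any of them.

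On model terms, section 5.3.2.1.1 says that x_j "is the vector denoting study treatments and covariates for subject j", but no covariate is named. The main relapse-rate model is fitted "with core study treatment as a factor and the logarithm of time in study (in years) from randomization" as offset, and the by-visit Gd+ T1 model "with core study treatment as a factor and no offset".

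**The concern.** An NB model is chosen because event counts usually vary more between subjects than Poisson allows. If the analysis moves to Poisson with model-based errors, that extra variation drops out of the standard error while the point estimate hardly changes. The interval then looks more precise than the data justify.

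This matters here because section 2 sets no hypotheses and calls all analyses exploratory. The 95% intervals are therefore the main statement of uncertainty around the model-based relapse and lesion rates, including the rate ratio of section 5.3.2.2.1.

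The lack-of-fit rule raises a separate question of logic: it offers as a repair a model that is a restricted form of the one found wanting.

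**Working it through.** **Inputs.** The SAP gives no dispersion, expected rate or interval width for any count model, so there is no figure to reproduce. All means (mu) and dispersions (k) below are assumptions, shown as ranges. The 877 enrolled subjects come from section 3; about 438 per core arm (877/2) is an assumption.

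**Interval width.** Under NB, Var(Y) = mu(1 + k·mu). For a log rate from n subjects with equal follow-up, the squared standard error is (1 + k·mu)/(n·mu), against 1/(n·mu) under Poisson. So

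- true SE / Poisson SE = sqrt(1 + k·mu)
- true coverage of a nominal 95% Poisson interval = 2Φ(1.96 / sqrt(1 + k·mu)) − 1

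| Setting | mu | k | SE ratio | Coverage |
|---|---|---|---|---|
| 24-week relapses | 0.05 | 1 | 1.02 | 94.4% |
| 24-week relapses | 0.10 | 1 | 1.05 | 93.8% |
| 24-week relapses | 0.15 | 1 | 1.07 | 93.2% |
| 24-week relapses, worst tried | 0.15 | 4 | 1.26 | 87.9% |
| Combined-period relapses | 1.2 | 1 | 1.48 | 81.4% |
| Lesions, mildest tried | 0.5 | 0.5 | 1.12 | 92.0% |
| Lesions | 2 | 2 | 2.24 | 61.9% |
| Lesions | 5 | 2 | 3.32 | 44.5% |

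Twenty-four weeks are 168/365.25 = 0.46 years, so means of 0.05 to 0.15 correspond to about 0.11 to 0.33 relapses per year.

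The 24-week rows apply to a planned analysis. The combined-period and lesion rows apply only if the fallback is triggered while the counts are still overdispersed.

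**When would the fallback be triggered?** One common cause of NB failure is a dispersion estimate at zero. Two-arm simulations used a dispersion score at k = 0 that is not positive as a proxy for this.

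| Per arm | Means | True k | Boundary reached | Poisson coverage when reached | Poisson coverage, all samples |
|---|---|---|---|---|---|
| 438 | 1.0 / 1.4 | 0 | 53% | 94% | 95% |
| 438 | 1.0 / 1.4 | 1 | never | – | 81% |
| 300 | 2 / 2 | 2 | never | – | 63% |
| 438 | 0.08 / 0.11 | 1 | 8% | 95% | 94% |
| 20 | 0.2 / 0.2 | 4 | 17% | 99% | 94.5% |

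Where the boundary is reached, plain Poisson is adequate. In the two clearly overdispersed settings with larger means it was never reached in 3,000 samples, so low coverage there would need NB to fail for another reason. The proxy does not measure how often that happens.

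**Lack of fit.** Poisson is NB with k fixed at 0, so the maximised NB likelihood is never below the Poisson one, and the two are equal when the estimated k is 0. If NB misfits through excess zeros, outliers or residual overdispersion, Poisson cannot do better. This needs no assumed figure.

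**Covariates.** Var(log rate ratio) = 2(1/mu + k)/n. If prognostic covariates remove a share s of k, interval width changes by sqrt[(1/mu + k(1 − s)) / (1/mu + k)].

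- mu 1.2, k 0.5, s 0.1: sqrt(1.283/1.333) = 0.981
- mu 5, k 2, s 0.3: sqrt(1.6/2.2) = 0.853

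Over the assumed inputs the intervals narrow by about 2% to 15%.

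**The case against.** The strongest defence is that the harmful combination may be rare. The fallback runs only on non-convergence, and when the cause is zero estimated dispersion Poisson is a sound substitute. A reader might infer that intervals are too narrow whenever the fallback is used; the documents and the simulations do not support that. Low coverage for lesion counts needs both strong overdispersion and NB failure for some other reason, and no probability can be put on the pair. This part of the defence stands.

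Where Poisson is certain, in the 24-week rates, the SAP gives its reason and the loss is usually one or two points of coverage. That stands too, but a robust variance would remove even this loss at almost no cost. In section 5.3.2.2.1 Poisson is only an example of what will be considered. The wording is soft, yet it is the only alternative named, and it cannot do the job.

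A reader might also take the missing covariates as an error, or adjustment as a cure for imbalance in the extension set (EXTS). Neither follows. The unadjusted NB models are valid, and the word covariates in section 5.3.2.1.1 can be read as generic notation that the endpoint sections then fill in. The relapse-rate models and the models for cumulative combined unique active lesions (CUAL) up to each visit are also run on the full analysis set, which keeps all randomized subjects. Section 5.1.5.1 concedes that the groups will differ at extension start. Entry into EXTS follows 108 weeks of core treatment, and core-baseline values cannot correct selection driven by events on treatment.

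**Conclusion.** The point holds in a limited form. The Poisson rules leave the intervals unprotected if overdispersion remains, and the lack-of-fit remedy is wrong in principle.

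For the planned 24-week rates the effect is small under most assumed inputs. For the fallback it ranges from nil, when the dispersion estimate is zero, to severe for overdispersed lesion counts whose NB model fails for other reasons; how often that would occur is unknown. Every coverage figure rests on assumed means and dispersions. Only the argument about lack of fit is free of them.

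Covariate adjustment is a matter of efficiency, not validity, and is the lesser part.

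**What to change.** 1. In sections 5.3.2.1.1 and 5.3.2.2.2, state that every Poisson fit, whether as fallback or for the 24-week rates, uses a robust (sandwich) or Pearson-scaled variance.
2. In section 5.3.2.2.1, delete Poisson as the remedy for lack of fit.
3. Optionally, name core-baseline covariates that are already collected: EDSS and pre-core relapse count for the relapse-rate models, and Gd+ T1 lesion count for the Gd+, T2 and CUAL models. Keep the unadjusted result alongside, and do not present the adjustment as correcting selection into EXTS. If none is wanted, drop the word from the definition of x_j. While editing, put the treatment factor into the example code, which now reads "model relnum_r = / dist=negbin link=log offset = log(Time") with nothing on the right-hand side.

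The cost is a few words and one or two options in the code. Some intervals will widen slightly, and adjusted models need a simple rule for missing covariates. The change does not rescue very sparse visits: in simulations with 20 subjects per arm and means of 0.1 to 0.2, at least one arm had no events in 4% to 27% of samples, and a log-rate interval then fails under either distribution.
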